5.5 Criteria for Taking a Participant Off Protocol Therapy

Duration of therapy will depend on individual response, evidence of disease progression and tolerance. In the absence of treatment delays due to adverse event(s), treatment may continue until one of the following criteria applies:

- Disease progression
- Intercurrent illness that prevents further administration of treatment
- Unacceptable adverse event(s)
- Treatment delay of > 21 days due to toxicity
- Participant demonstrates an inability or unwillingness to comply with the medication regimen and/or documentation requirements
- Participant decides to withdraw from the protocol therapy
- General or specific changes in the participant's condition render the participant unacceptable for further treatment in the judgment of the treating investigator

Participants will be removed from the protocol therapy when any of these criteria apply. The reason for removal from protocol therapy, and the date the participant was removed, must be documented in the case report form (CRF) and entered in the Clinical Trial Management System (OnCore). Alternative care options will be discussed with the participant.

In the event of unusual or life-threatening complications, treating investigators must immediately notify [name] MPH at [contact].

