5.6 Duration of Follow Up

Participants will be followed on-study until progression or death, whichever occurs first. Participants removed from protocol therapy for unacceptable adverse event(s) will be followed until resolution or stabilization of the adverse event.

The participant's treatment status will be updated in OnCore at the time treatment with cisplatin and AZD1775 is discontinued.

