6.1 Dose Delays and Modifications for AZD1775

Participants can have a maximum of 2 dose modifications (if applicable) throughout the course of the study for toxicities. Participants who require more than 2 dose modifications may remain on study and continue with cisplatin monotherapy per investigator discretion. In the event that a participant is not willing to dose reduce AZD1775, they may continue with cisplatin monotherapy per investigator discretion.

In the event of toxicity, it is recommended that the investigator first modify the dose of AZD1775; however the investigator may choose to first modify the chemotherapy dose instead, in consultation with the Principal Investigator. If a second dose reduction is necessary during combination therapy, the dose of chemotherapy or AZD1775 may be modified. This decision should be made jointly by the treating physician and the Principal Investigator. Participants who experience toxicity that the investigator finds attributable to AZD1775 will have their AZD1775 dose reduced by 1 dose level as shown in Table 6-1. A participant's dose may be re-escalated at the discretion of the principal investigator.

If Day 1 dosing is delayed, all assessments will be delayed to accordingly.

Table 6-1 DOSE MODIFICATION OF AZD1775

Dose Level	AZD1775 Dose
0	200mg, twice daily x 5 doses
-1	175mg, twice daily x 5 doses
-2	150mg, twice daily x 5 doses
-3	125mg, twice daily x 5 doses

Nausea	Management/Next Dose for AZD1775
≤ Grade 1	No change in dose
Grade 2	Hold until ≤ Grade 1. Resume at same dose level.
Grade 3	Hold* until < Grade 2. Resume at one dose level lower, if indicated.**
Grade 4	Discontinue treatment and follow for disease progression
4	

^{*}Participants requiring a delay of >3 weeks should discontinue AZD1775.

All patients must receive a 5-HT3 antagonist prior to each dose of AZD1775. Additional doses of 5-HT3 antagonist may be used if needed. In addition, dexamethasone 4 mg PO will be given with each AZD1775 dose as a minimum on the first day of dosing AZD1775 of every 3-5 days dosing period, unless contraindicated or not well-tolerated. Dexamethasone may be continued on further days of dosing, potentially at a lower dose. Dexamethasone or the 5-HT3 antagonist may be given by IV.

Promethazine (Phenergan), prochlorperazine (Compazine), and benzodiazepine may still be used as additional adjunctive treatments during AZD1775 therapy.

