*Participants requiring a delay of >3weeks should discontinue AZD1775.		
**Participants requiring > two dose reductions should discontinue AZD1775.		

Other Non- Hematologic Toxicities	Management/Next Dose for AZD1775	
Grade 1	No change in dose	
Grade 2^	Hold until ≤ Grade 1. Resume at same dose level.	
Grade 3	Hold until < Grade 2. Resume at one dose level lower, if indicated.	
Grade 4	Hold until < Grade 2. Resume at one dose level lower, if indicated.	

- Dose modifications for AZD1775 non-hematologic toxicities should be based on toxicities occurring during the previous cycle.
- For toxicities that lead to a dose reduction, the dose will not be re-escalated during subsequent cycles.
- Any patient who develops a Grade 3 or 4 nonhematologic toxicity that does not resolve to ≤ Grade 1 within 3 weeks should discontinue AZD1775, unless approved by the Principle Investigator.
- Participants requiring > two dose reductions, should discontinue AZD1775.
- ^intolerable Grade 2

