Ototoxicity has been observed in up to 31% of subjects treated with a single dose of cisplatin (50mg/m²) and is manifested by tinnitus and/or hearing loss in the high frequency range (4000 to 8000 Hz). Decreased ability to hear normal conversational tones may occur occasionally. Ototoxicity can be more severe in children than in adults and more frequent and severe with repeated administration. Hearing loss can be unilateral or bilateral and is usually not reversible. During treatment with cisplatin, it is necessary to monitor hearing at each visit as part of a standard physical exam.

Myelosuppression

Myelosuppression occurs in 25 to 30% of subjects treated with cisplatin. The nadirs in circulating platelets and leukocytes occur between days 18 and 23, with most subjects recovering by day 39. Leukopenia and thrombocytopenia are more pronounced at higher doses (>50 mg/m²). Anemia (a decrease in hemoglobin of 2 gm/100ml) occurs at approximately the same frequency and with the same timing as leukopenia and thrombocytopenia.

Neurotoxicity

Cisplatin neurotoxicity is characterized by peripheral neuropathies, which are sensory in nature but can also include motor difficulties such as reduced deep-tendon reflexes and leg weakness. The symptoms usually occur after prolonged therapy (4 to 7 months). Cisplatin therapy should be discontinued when serious neuropathy develops. The neuropathy, however, may progress

further even after discontinuation of treatment.

Hematologic Toxicity

Dose adjustment at the start of a subsequent cycle of therapy will be based on the neutrophil and platelet counts on day 1 of the cycle. ANC must be $\geq 1.0 \times 10^9 / L$ and platelets $\geq 75 \times 10^9 / L$ before the start of each cycle. Treatment should be delayed to allow sufficient time for recovery. Upon recovery, if treatment is resumed, it should be accounting to the guidelines in Table 6-2 with respect to nadir platelet and ANC values for subsequent cycles, except as noted below. A delay in treatment due to hematologic toxicity if more than 3 weeks will result in withdrawal from the study.

The use of colony stimulating factors (filgrastim or pegfilgrastim) is permissible if recommended by the primary treating physician but should be clearly recorded in the medical record and case report form. Prophylactic use of GCSF is not recommended with the first cycle.

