Patients who develop treatment-related grade 3 non-hematological toxicity (except grade 3 transaminase elevations and nausea or vomiting) should have cisplatin therapy delayed until toxicity has resolved to less than or equal to grade 1 or baseline. Cisplatin will be continued at 60mg/m² for subsequent cycles. For grade 3 nausea, vomiting, or transaminase elevation, treatment will be delayed until toxicity resolves to grade 1 or less, and treatment may resume at 75 mg/m² dose. If any toxicity, including those described above, results in a three week treatment delay, patients will be taken off protocol. Patients with grade 4 non-hematological toxicity attributed to cisplatin will come off study unless exception is given by the Protocol Chair. Prior to retreatment, toxicity must resolve to less than or equal to grade 1 or baseline. For ≥ grade 2 Hgb toxicity, at the treating physician's discretion, dose may be reduced by one dose level in addition to transfusions and/or growth factor support as clinically indicated, with the option to re-escalate at physician's discretion. This should be documented in the medical record.

Table 6-6: Cisplatin Toxicity Management and Dose Modification Summary Table

Toxicity Event	Dose Modification	
Hematologic		
$ANC > 1000/mm^3$	None	
$ANC \geq 500/mm^3$	Delay until >1000/mm ³ and reduce to 60mg/m ²	
	(treat at 75mg/mm ² if initiating GCSF)	
$ANC < 500/mm^3$	Delay until >1000/mm ³ and reduce to 50mg/m ²	
	(treat at 60mg/mm ² if initiating GCSF)	
Grade 3 or 4 toxicity	Withdrawal from study or continue	
after 2 dose reduction		
Plt >100,000/mm ³	None	
Plt >50,000/mm ³	Delay until >75,000/mm ³ and reduce to 60mg/m ²	
$Plt < 50,000/mm^3$	Delay until >75,000/mm ³ and reduce to 50mg/m ²	
C 1 2 4	W'.1.11.C	
Grade 3 or 4 toxicity	Withdrawal from study	
after dose reduction		
Gastrointestinal		
Diarrhea		
Grade 3/4 or	Delay until resolution and reduce to 60mg/m ²	
requiring hospitalization		
Vomiting, Nausea		
Grade 3/4	Delay until ≤grade 1 or has returned to baseline and resume at	
	75mg/m ² or with one dose reduction (Per investigator discretion)	
Transaminases		
Grade 3/4	Delay until ≤grade 2 and with one dose reduction	
Neurological		
Neurosensory		
Grade 0-1	None	
Grade 2	Delay until resolves to ≤grade 1 and resume with one dose reduction	
Grade 3-4	Withdrawal from study	
Ototoxicity		
Tinnitus or	Reduce dose or withdraw from study at investigator discretion	
significant hearing loss		
Nephrotoxicity		
Cr <1.6 mg/dl or	None	

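### A toxicity delay of about three weeks ends all protocol therapy under 5.5, AZD1775 only under 6.1 and study participation under 6.2, and nothing says which rule governs

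*Combined protocol and SAP*

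**What the plan says.** Four rules in the protocol respond to a toxicity delay of about three weeks.

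- Section 5.5 lists "Treatment delay of > 21 days due to toxicity" and adds: "Participants will be removed from the protocol therapy when any of these criteria apply". It names no agent and gives no exception.
- Section 6.1, in the footnotes to the nausea, vomiting, diarrhea, neutropenia and thrombocytopenia tables, says: "Participants requiring a delay of >3 weeks should discontinue AZD1775". Cisplatin is not mentioned.
- Section 6.2, under Hematologic Toxicity, says: "A delay in treatment due to hematologic toxicity if more than 3 weeks will result in withdrawal from the study".
- Section 6.2, under Other Toxicity, covers any toxicity: "results in a three week treatment delay, patients will be taken off protocol".

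Two sections define what happens afterwards. Section 5.6 keeps participants on-study until they progress or die, and says: "Participants removed from protocol therapy for unacceptable adverse event(s) will be followed until resolution or stabilization of the adverse event". Section 5.7 gives four reasons for leaving the study: progression, loss to follow-up, withdrawal of consent for data submission, and death.

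The protocol also allows treatment with one drug. Section 6.1 lets a patient who needs more than two dose modifications stay on cisplatin alone. Section 6.2 lets a patient who must stop cisplatin stay on AZD1775 alone.

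**The concern.** One event carries different consequences depending on the section a site consults. Under one rule all treatment ends and follow-up continues. Under another only AZD1775 stops, which leaves cisplatin open. Under a third the patient leaves the study. Sites that each comply with the protocol could therefore treat, classify and follow similar patients differently, and these are patients with prolonged toxicity.

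At stake are the treatment these patients go on to receive, the off-therapy or off-study status and date entered in the CRF and OnCore, the scan schedule that applies, and whether unresolved toxicity is followed to its end.

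**Working it through.** No power or error-rate calculation applies. The check sets the rules side by side.

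**Step 1: put the thresholds in one unit.** 3 weeks × 7 = 21 days. Section 5.5, the 6.1 footnotes and the hematologic rule in 6.2 therefore share one threshold, more than 21 days. The Other Toxicity rule in 6.2 is met when the delay reaches 21 days.

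**Step 2: apply them to neutropenia that delays a combination cycle.**

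| Rule | Delay of exactly 21 days | Delay of 22 days |
|---|---|---|
| 5.5 | not met | off protocol therapy, no agent named |
| 6.1 footnote | not met | AZD1775 stops |
| 6.2 Hematologic Toxicity | not met | withdrawn from the study |
| 6.2 Other Toxicity | off protocol | off protocol |

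At 22 days all four rules apply. No section ranks them.

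**Step 3: ask whether one delay involves both drugs.** Section 5.2.2 sets a single list of criteria for starting each later cycle. Section 5.3.1 starts AZD1775 together with cisplatin on day 1. A neutrophil count that fails the 5.2.2 criterion therefore holds back both drugs, and the AZD1775 rule and the whole-regimen rule are triggered together.

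**Step 4: compare with the off-study list.** Sections 5.5 and 5.7 treat off-therapy and off-study as separate states, and each requires its own reason and date. A site applying the hematologic rule in 6.2 literally would record an off-study reason that 5.7 does not contain, for a patient whom 5.6 keeps on-study.

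**Step 5: work out the effect on scans (Section 10, footnote h).**
- On treatment: every 2 cycles, 2 × 21 = 42 days = 6 weeks, ± 7 days, so 5 to 7 weeks.
- Held or delayed but still treated: scans follow cycles received. One 22-day delay within a two-cycle interval gives 42 + 22 = 64 days, about 9.1 weeks, before the ± 7 days.
- Off study without progression: every 6 to 9 weeks until progression.

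The status recorded decides which schedule applies. The gap is not always longer in one direction. All these intervals exceed the 4-week minimum for confirming a response in 11.1.4.4.

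**Step 6: check neighbouring stopping rules.** After grade 3–4 neurosensory toxicity, Table 6-4 offers AZD1775 alone as an alternative to withdrawal, while Table 6-6 lists only withdrawal from study. Section 6.1 stops AZD1775 when more than two reductions are needed, yet Table 6-1 lists a third reduction level, -3.

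**The case against.** The best defence is scope. Section 6.1 is headed and worded for AZD1775, while 5.5 speaks of treatment and protocol therapy, so 6.1 may govern a hold of AZD1775 alone and 5.5 a delay of the whole regimen. This is a reasonable reading, but the text does not state it, and it leaves the study withdrawal in 6.2 in conflict with 5.5, 5.6 and 5.7. A second defence is that withdrawal from the study in 6.2 is loose wording for stopping treatment. Tables 6-3 and 6-4 give that some support, since they offer AZD1775 alone as the alternative. Those entries are not triggered by a delay, however, and 5.5 and 5.7 keep the two states apart.

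Several stronger inferences are tempting and do not stand:

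- *Outcome data are lost.* Footnote h asks for scans until progression after a patient leaves the study. Best response runs to progression (11.1.4.4), and every treated patient stays in the analysis (13.2, 13.4.2). For toxicity there is an end-of-treatment adverse-event assessment (Section 10), SAE reporting to 30 days after the last dose (7.2.1) and submission of SAE follow-up information (7.4). The exposure lies mainly in non-serious events still unresolved.
- *The go/no-go decision at 11 of 37 responses is threatened.* The documents give no rate of such delays, and nothing in them shows a response being gained or lost through this conflict.
- *Investigator approval is a further answer to a delay.* The clause "within 3 weeks should discontinue AZD1775, unless approved by the Principle Investigator" is triggered by grade 3–4 non-hematologic toxicity that has not resolved. AZD1775 is taken over 2.5 days of a 21-day cycle, so a toxicity can last three weeks with little or no dosing delay.
- *These are the only patient-level stopping rules.* Section 5.5 lists six other criteria, and the toxicity tables contain grade-based stops.

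The 21-day edge case is minor in itself, given the ± 3-day scheduling window.

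**Conclusion.** The contradiction is in the current text. For a hematologic delay of more than 21 days the protocol gives three distinct consequences (off protocol therapy, off AZD1775 only, out of the study), plus a fourth rule with a slightly different threshold and the undefined term off protocol. Reading 6.1 as specific to AZD1775 narrows the conflict but does not remove it.

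The effect is confined to treatment received, recorded status, scan timing and follow-up of unresolved toxicity. The analysis population and the two-stage design figures are unaffected. How many patients would be involved cannot be derived from the documents.

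Two assumptions matter. The 6.2 wording is taken at face value. Removal for a toxicity delay is taken to fall under the adverse-event follow-up in 5.6, although 5.5 lists delay and unacceptable adverse events as separate criteria.

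**What to change.** - Reconcile 5.5, the 6.1 table footnotes and the unresolved-toxicity bullet in 6.1, and the Hematologic Toxicity and Other Toxicity rules in 6.2 into one delay rule. It should state its threshold and which agent or agents it stops, keep delay distinct from unresolved toxicity, and be cross-referenced from the other sections.
- Reconcile the withdrawal wording in 6.2 and Tables 6-3, 6-4 and 6-6 with 5.6 and 5.7, so that off-therapy and off-study each have one meaning throughout. This includes the difference between Tables 6-4 and 6-6 after grade 3–4 neurosensory toxicity.
- Reconcile level -3 in Table 6-1 with the two-reduction limit in 6.1.

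The clinical content of each rule is for the sponsor to decide. The cost is a protocol wording amendment, with no added visits, staff or patients.

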5.6 Duration of Follow Up

Participants will be followed on-study until progression or death, whichever occurs first. Participants removed from protocol therapy for unacceptable adverse event(s) will be followed until resolution or stabilization of the adverse event.

The participant's treatment status will be updated in OnCore at the time treatment with cisplatin and AZD1775 is discontinued.

5.7 Criteria for Taking a Participant Off Study

Participants will be removed from study when any of the following criteria apply:

- Disease Progression (in patients who come off treatment for reasons other than progressive disease)
- Lost to follow-up
- Withdrawal of consent for data submission
- Death

The reason for taking a participant off study, and the date the participant was removed, must be documented in the case report form (CRF) and Clinical Trial Management System (OnCore).

6. DOSING DELAYS/DOSE MODIFICATIONS

Dose delays and modifications will be made as indicated in the following table(s). The descriptions and grading scales found in the revised NCI Common Terminology Criteria for Adverse Events (CTCAE) version 4.0 will be utilized for dose delays and dose modifications. A copy of the CTCAE version 4.0 can be downloaded from the CTEP website http://ctep.cancer.gov/protocolDevelopment/electronic applications/ctc.htm.

6.1 Dose Delays and Modifications for AZD1775

Participants can have a maximum of 2 dose modifications (if applicable) throughout the course of the study for toxicities. Participants who require more than 2 dose modifications may remain on study and continue with cisplatin monotherapy per investigator discretion. In the event that a participant is not willing to dose reduce AZD1775, they may continue with cisplatin monotherapy per investigator discretion.

In the event of toxicity, it is recommended that the investigator first modify the dose of AZD1775; however the investigator may choose to first modify the chemotherapy dose instead, in consultation with the Principal Investigator. If a second dose reduction is necessary during combination therapy, the dose of chemotherapy or AZD1775 may be modified. This decision should be made jointly by the treating physician and the Principal Investigator. Participants who experience toxicity that the investigator finds attributable to AZD1775 will have their AZD1775 dose reduced by 1 dose level as shown in Table 6-1. A participant's dose may be re-escalated at the discretion of the principal investigator.

If Day 1 dosing is delayed, all assessments will be delayed to accordingly.

Table 6-1 DOSE MODIFICATION OF AZD1775

Dose Level	AZD1775 Dose
0	200mg, twice daily x 5 doses
-1	175mg, twice daily x 5 doses
-2	150mg, twice daily x 5 doses
-3	125mg, twice daily x 5 doses

Nausea	Management/Next Dose for AZD1775
≤ Grade 1	No change in dose
Grade 2	Hold until ≤ Grade 1. Resume at same dose level.
Grade 3	Hold* until < Grade 2. Resume at one dose level lower, if indicated.**
Grade 4	Discontinue treatment and follow for disease progression
4	

^{*}Participants requiring a delay of >3 weeks should discontinue AZD1775.

All patients must receive a 5-HT3 antagonist prior to each dose of AZD1775. Additional doses of 5-HT3 antagonist may be used if needed. In addition, dexamethasone 4 mg PO will be given with each AZD1775 dose as a minimum on the first day of dosing AZD1775 of every 3-5 days dosing period, unless contraindicated or not well-tolerated. Dexamethasone may be continued on further days of dosing, potentially at a lower dose. Dexamethasone or the 5-HT3 antagonist may be given by IV.

Promethazine (Phenergan), prochlorperazine (Compazine), and benzodiazepine may still be used as additional adjunctive treatments during AZD1775 therapy.

Please note: aprepitant [Emend] and fosaprepitant are not permitted due to known DDIs.

Patients should be strongly encouraged to maintain liberal oral fluid intake.

Suitable alternative medications may be used, with adequate justification, where the use of any of the above medications might interfere with other study procedures or are deemed insufficient.

^{**}Participants requiring > two dose reductions should discontinue AZD1775

Vomiting	Management/Next Dose for AZD1775
≤ Grade 1	No change in dose
Grade 2	Hold until ≤ Grade 1. Resume at same dose level.
Grade 3	Hold* until < Grade 2. Resume at one dose level lower, if indicated.**
Grade 4	Discontinue treatment and follow for disease progression

^{*}Participants requiring a delay of >3 weeks should discontinue AZD1775.

All patients must receive a 5-HT3 antagonist prior to each dose of AZD1775. Additional doses of 5-HT3 antagonist may be used if needed. In addition, dexamethasone 4 mg PO will be given with each AZD1775 dose as a minimum on the first day of dosing AZD1775 of every 3-5 days dosing period, unless contraindicated or not well-tolerated. Dexamethasone may be continued on further days of dosing, potentially at a lower dose. Dexamethasone or the 5-HT3 antagonist may be given by IV.

Promethazine (Phenergan), prochlorperazine (Compazine), and benzodiazepine may still be used as additional adjunctive treatments during AZD1775 therapy.

Please note: aprepitant [Emend] and fosaprepitant are not permitted due to known DDIs.

Patients should be strongly encouraged to maintain liberal oral fluid intake.

Suitable alternative medications may be used, with adequate justification, where the use of any of the above medications might interfere with other study procedures or are deemed insufficient.

Diarrhea	Management/Next Dose for AZD1775
≤ Grade 1	No change in dose
Grade 2	Hold until ≤ Grade 1. Resume at same dose level.
Grade 3	Hold* until < Grade 2. Resume at one dose level lower, if indicated.**
Grade 4	Discontinue treatment and follow for disease progression
 b	

^{*}Participants requiring a delay of >3 weeks should discontinue AZD1775.

Recommended management: Loperamide antidiarrheal therapy

Dosage schedule: 4 mg at first onset, followed by 2 mg with each loose motion until diarrheafree for 12 hours (maximum dosage: 16 mg/24 hours)

Adjunct anti-diarrheal therapy is permitted and should be recorded when used.

Participants should be instructed to notify their research doctor for the occurrence of blood or black stools, symptoms of dehydration, fever, inability to take liquids by mouth, and inability to control diarrhea within 24 hours of using loperamide or other prescribed antidiarrheal medications.

If associated with severe (Grade 3 or 4) neutropenia, broad-spectrum antibiotics must be prescribed. Patients should be considered for hospitalization for IV hydration and correction of electrolytes.

^{**}Participants requiring > two dose reductions should discontinue AZD1775.

^{**}Participants requiring > two dose reductions should discontinue AZD1775.

Neutropenia	Management/Next Dose for AZD1775			
≤ Grade 1	No change in dose			
First occurrence	$Hold^*$ until \leq Grade 1. Resume at same dose level.			
Grade 2				
Second or Third	Hold* until \leq Grade 1. Resume at one dose level lower, if indicated**			
Occurrence Grade 2;				
First Occurrence	Hold* until \leq Grade 1. Resume at one dose level lower, if indicated**			
Grade 3 or Second				
Occurrence Grade 3				
Grade 3 Febrile	Hold* until \leq Grade 1. Resume at one dose level lower, if indicated**			
Neutropenia or				
Grade 3 Neutropenia				
with documented				
infection.				
Grade 4 or Second	Hold* until \leq Grade 1. Resume at one dose level lower, if indicated**			
Occurrence Grade 4				
Grade 4 Febrile	Discontinue.			
Neutropenia or				
Grade 4 Neutropenia				
with documented				
infection.				
*Participants requiring	a delay of >3 weeks should discontinue AZD1775.			
**Participants requiring	**Participants requiring > two dose reductions should discontinue AZD1775.			

Note: Consider using G-CSF per institutional standards for neutropenia or febrile neutropenia.

Thrombocytopenia	Management/Next Dose for AZD1775	
≤ Grade 1	No change in dose	
First Occurrence	$Hold^*$ until \leq Grade 1. Resume at same dose level.	
Grade 2		
Second or Third	$Hold^*$ until \leq Grade 1. Resume at one dose level lower, if indicated**	
Occurrence Grade 2		
First Occurrence	$Hold^*$ until \leq Grade 1. Resume at one dose level lower, if indicated**	
Grade 3 or Second		
Occurrence Grade 3		
First or Second	$Hold^*$ until \leq Grade 1. Resume at one dose level lower, if indicated**	
Occurrence Grade 4		
without any evidence		
of bleeding		
Thrombocytopenia	Discontinue.	
haemorrhage (gross		
occult bleeding)		
associated with		
platelet count		
<50,000 uL		

Thrombocytopenia	Management/Next Dose for AZD1775	
*Participants requiring a delay of >3weeks should discontinue AZD1775.		
**Participants requiring > two dose reductions should discontinue AZD1775.		

Other Non- Hematologic Toxicities	Management/Next Dose for AZD1775	
Grade 1	No change in dose	
Grade 2^	Hold until ≤ Grade 1. Resume at same dose level.	
Grade 3	Hold until < Grade 2. Resume at one dose level lower, if indicated.	
Grade 4	Hold until < Grade 2. Resume at one dose level lower, if indicated.	

- Dose modifications for AZD1775 non-hematologic toxicities should be based on toxicities occurring during the previous cycle.
- For toxicities that lead to a dose reduction, the dose will not be re-escalated during subsequent cycles.
- Any patient who develops a Grade 3 or 4 nonhematologic toxicity that does not resolve to ≤ Grade 1 within 3 weeks should discontinue AZD1775, unless approved by the Principle Investigator.
- Participants requiring > two dose reductions, should discontinue AZD1775.
- ^intolerable Grade 2

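### Section 6.1 gives conflicting AZD1775 dosing instructions: an ungraded one-level cut against tables that keep the dose at grades 1 and 2, and two different re-escalation rules

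*Combined protocol and SAP*

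**What the plan says.** **General rule.** The text of Section 6.1, ahead of the tables, says that those who experience "toxicity that the investigator finds attributable to AZD1775 will have their AZD1775 dose reduced by 1 dose level", by reference to Table 6-1. That table lists dose levels 0 to -3 and contains no grades. The same paragraph is mainly about which drug to modify first: AZD1775 is recommended, but "the investigator may choose to first modify the chemotherapy dose instead, in consultation with the Principal Investigator".

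**Toxicity tables.** Six tables follow: nausea, vomiting, diarrhea, neutropenia, thrombocytopenia and other non-hematologic toxicities. All six leave the dose unchanged at grade 1. For grade 2 nausea, vomiting and diarrhea, and for other non-hematologic grade 2 events (footnoted as intolerable grade 2), the instruction is "Hold until ≤ Grade 1. Resume at same dose level". For a first grade 2 neutropenia or thrombocytopenia it is again to hold and then "Resume at same dose level".

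**Lead-in.** Section 6 opens by saying that delays and modifications follow the tables, graded by CTCAE version 4.0. It does not say which prevails if table and text differ.

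**Cap.** "Participants can have a maximum of 2 dose modifications (if applicable) throughout the course of the study for toxicities".

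**Re-escalation.** The opening text of Section 6.1 says that a participant's "dose may be re-escalated at the discretion of the principal investigator". A bullet under the table for other non-hematologic toxicities says that, once a toxicity has led to a reduction, the dose is not raised again in later cycles.

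**The concern.** The general sentence is mandatory and ungraded. For a grade 1 event, or a grade 2 event in the rows above, that the investigator attributes to AZD1775, the sentence calls for a one-level cut and the table row calls for the same dose level. Both cannot be followed. A site that keeps 200 mg after attributed grade 2 nausea complies with the table and departs from the sentence; a site that cuts to 175 mg does the reverse. A monitor has no stated rule for deciding which is the deviation.

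At stake is consistent dosing of the investigational drug. An unneeded cut counts toward a cap of two modifications, and the table footnotes stop AZD1775 in participants who need more than two reductions. Whether a cut can be reversed also has two answers, at least for other non-hematologic toxicities.

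**Working it through.** The plan states no figure on this point, so there is none to reproduce. The check is a count of table rows, one dose calculation and a comparison of texts.

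**1. Row count.** Inputs: the six AZD1775 tables in Section 6.1, with wrapped lines joined and the repeated thrombocytopenia header not counted.

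| Table | Rows | Keep dose level | One level lower, if indicated | Discontinue |
|---|---|---|---|---|
| Nausea | 4 | 2 | 1 | 1 |
| Vomiting | 4 | 2 | 1 | 1 |
| Diarrhea | 4 | 2 | 1 | 1 |
| Neutropenia | 7 | 2 | 4 | 1 |
| Thrombocytopenia | 6 | 2 | 3 | 1 |
| Other non-hematologic | 4 | 2 | 2 | 0 |
| Total | 29 | 12 | 12 | 5 |

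12 + 12 + 5 = 29. The 12 keep-level rows are six at grade 1 (no change) and six at grade 2 (hold, then the same level). These 12 are where sentence and table conflict. The 12 conditional-reduction rows use the same one-level step and the 5 discontinue rows are explicit; neither group is part of this point.

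**2. Size of one step.** Five doses per course: 5 × 200 mg = 1,000 mg at level 0; 5 × 175 mg = 875 mg at level -1. (1,000 - 875) / 1,000 = 12.5%. One of two permitted modifications is then used.

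**3. Comparison with cisplatin.** The corresponding sentence in Section 6.2 has the same structure but applies only to grade 3 or 4 toxicity attributable to cisplatin. The AZD1775 sentence lacks that qualifier.

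**4. Where the tables are silent.** The grade 2 row for other non-hematologic toxicity is limited to intolerable events, so a tolerable grade 2 event of that kind has no row. Section 5.2.2 requires recovery to grade 1 or less before the next cycle but sets no AZD1775 dose level. There the ungraded sentence is the only dose-level instruction, and no row contradicts or overrides it.

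**5. Re-escalation.** The permission in the opening text is unrestricted by toxicity. The prohibition sits under the other non-hematologic table, directly after a bullet limited to that class: "Dose modifications for AZD1775 non-hematologic toxicities should be based on toxicities occurring during the previous cycle". Its own wording does not name a class. On the narrow reading the two texts conflict for other non-hematologic toxicities; on the broad reading they conflict for every toxicity-driven reduction.

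**The case against.** The best reply is that the document largely settles the first conflict. The Section 6 lead-in directs modifications to the tables, and a specific row ordinarily controls a general sentence. The sentence also sits in a paragraph about which drug to modify and cites a table containing only dose levels, so it was probably meant to fix the drug and the step size. Read literally, it would force a cut for grade 1 nausea and sit oddly with the discontinue rows, which a trained investigator would be unlikely to accept. The re-escalation bullet can likewise be read as a specific exception to a general permission.

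Much of this stands: the intended reading is probably that the tables govern. But the intention is not written down. No precedence is stated, Table 6-1 is itself one of the tables that follow the lead-in, and the tables leave tolerable grade 2 other non-hematologic toxicity uncovered. The exception reading of the bullet is reasonable, but the permission does not mention an exception.

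A reader might also infer that the protocol requires a cut for any toxicity whatever, or that 12 of 29 rows (41%) means a similar share of events or patients would be wrongly dosed. The documents support neither. The sentence says toxicity, not any toxicity, and its context points to a narrower purpose. Rows are not events, patients or doses; two keep-level rows per table simply reflect a grade 1 line and a grade 2 line.

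**Conclusion.** Section 6.1 is internally inconsistent as written, on two matters: the dose level after attributed grade 1 and certain grade 2 events, and re-escalation after a reduction. This is a wording fault in the dosing rules rather than a questionable design decision, and it should be corrected.

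Its consequence is conditional. If a site follows the sentence over the table row, one event costs 12.5% of the AZD1775 course dose and one of two modifications. The documents do not say how often that would occur. It would also be tempting to infer damage to the objective response rate or to the study's power. Nothing supports that: the Section 13.1 design rests on response rates of 20% and 40%, with no dose-intensity term, and the documents give no relation between a 25 mg step and response. Nor is safety harm shown, since the postulated error lowers the dose.

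The conclusion assumes that toxicity without a grade includes grades 1 and 2, which is its plain meaning, and that the re-escalation bullet covers at least the table under which it appears.

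**What to change.** Replace the general sentence in Section 6.1 with: *AZD1775 is modified according to the toxicity tables below; when a reduction is required, reduce by 1 dose level as shown in Table 6-1.* Under this wording a tolerable grade 2 other non-hematologic event, which has no row, triggers no reduction; if the sponsor intends otherwise, a row should be added.

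Add to the re-escalation sentence: *except after reductions for other non-hematologic toxicities, which are not re-escalated.* If the prohibition was meant for all toxicities, delete the permission instead.

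The cost is a two-sentence protocol clarification, with no added procedures, visits or patients.
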